8.1.1.3 Serious AE or Serious Suspected Adverse Reaction

An AE or suspected adverse reaction is considered “serious” if any of the following criteria is met:

- Death, including death that appear unrelated to the study treatment
- Life-threatening AE
- Inpatient hospitalization or prolongation of an existing hospitalization, excluding the following scenarios:
 - i. Emergency room visit or hospital visit without official admission

- ii. Prolongation due to management or progression of the underlying disease
 - iii. Hospitalization for a pre-existing condition, provided that any of the following criteria are met:
 1. The hospitalization was planned
 2. Hospitalization to accommodate study treatment administration or required study procedures
 3. Hospitalization due to disease progression
- Persistent or significant disability/incapacity
 - Congenital anomaly/birth defect
 - Important medical events that may not result in death, be life-threatening, or require hospitalization may be considered serious when, based upon appropriate medical judgment, they may jeopardize the patient and may require medical or surgical intervention to prevent one of the outcomes listed in this definition. Examples of such medical events include allergic bronchospasm requiring intensive treatment in an emergency room or at home, blood dyscrasias or convulsions that do not result in inpatient hospitalization, or the development of drug dependency or drug abuse.

8.1.1.4 *Unexpected AE or Unexpected Suspected Adverse Reaction*

An AE or suspected adverse reaction is considered “unexpected” if it is not reported in nature, severity or incidence in the current version of the pracinostat IB (Section 7. Appendix).

8.1.1.5 *Treatment-Emergent Adverse Event*

A TEAE is an adverse event that emerges, or a pre-existing adverse event that worsens in severity, any time after the patient receives Dose 1 of study drug (pracinostat/placebo) through the end of the AE reporting period. AEs with onset before the patient receives Dose 1 of study drug are considered as pre-treatment AEs. AEs with onset after the end of the reporting period (if any) are considered as post-treatment AEs.

Laboratory tests, vital signs, and ECG abnormalities will be reported as AEs only if the event is considered clinically significant or leads to medical intervention (e.g., additional concomitant medication or procedures, discontinuation of study drug). Refer to Section [8.2.5.3](#) for details.

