8.2 Adverse Event Reporting

All adverse events occurring from the informed consent signature until 30 calendar days after last study drug (pracinostat/placebo) intake, or until the initiation of new therapy for AML, whichever occurs first, are to be recorded on the appropriate eCRF section.

Every effort must be made by the Investigator to categorize each adverse event according to its severity and its relationship to the study treatment (study drug and/or azacitidine).

All AEs will be followed until symptom resolution or until the condition stabilizes, unless, in the Investigator's opinion, the AE or laboratory abnormality/ies are not likely to improve because of the underlying disease or unless the patient is lost to follow-up.

Whenever a change in the severity of an AE (such as a worsening) has occurred, a follow up of the initial AE should be entered in the eCRF reporting the new severity.

Outcome of ongoing serious and non-serious AEs will be reported in eCRF until the end of the reporting period as above defined. All non-resolved serious and non-serious AEs beyond such date will be recorded in eCRF as "ongoing" without further follow-up.

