Each TEAE is collected in the eCRF by recording one initial record and one record for each change in seriousness and/or severity within the same occurrence of the event. A summary record will be derived aimed at being used for the production of the summary tables, while individual records will only be listed.

The summary record will pick-up among the collected records relevant to the same event (it is allowed to collect one field from one record and another field from another record) the maximum seriousness and the maximum severity. Actions taken will be picked up from all the records in order to keep all the actions taken with the event. The outcome will be picked up from the last record in time-sequential order. The relationship will be reconciled during data cleaning, so it will be the same in all of the records related to the same event at time of analysis.

As MRD (positive/negative) will be obtained together with the other data related to MRD analyses from the external lab, CR_{MRD} will be derived in the CDISC datasets from CR and MRD results.

Adverse events of special interest (as described in the study protocol) will be retrieved according to the following rules reported in the table:

AESI	MedDRA SMQ (v.20.0)	MedDRA PT (v. 20.0)	Comments
QTc prolongation	Torsade de Pontes/QT prolongation (SMQ) - NARROW	n/a	
Supraventricular arrhythmias	Supraventricular tachyarrhythmias (SMQ) - NARROW	n/a	
Sepsis, septic shock, grade ≥ 3 lung infection (pneumonia), any infection leading to death	Toxic-septic shock conditions (SMQ) - NARROW	1.Any PT that includes the word sepsis 2.Exact match to the PT pneumonia or lung infection	Pneumonia only if grade ≥ 3

Grade ≥ 3 anemia, neutropenia, febrile neutropenia and thrombocytopenia	n/a	
1.Any PT that includes the word anaemia.
 
2.Exact match to any of the following PTs:
 
Haemoglobin decreased Band neutrophil count decreased Band neutrophil percentage decreased Febrile neutropenia Granulocyte count decreased Granulocytopenia Neutropenia Neutropenic infection Neutropenic sepsis Neutropenic colitis Neutrophil count decreased Neutrophil percentage decreased Platelet count decreased Platelet production decreased Thrombocytopenia Febrile bone marrow aplasia
	All listed PTs only if grade ≥ 3
Grade ≥ 3 haemorrhage	n/a	Any PT that includes the word haemorrhage or haematoma or bleeding	All listed PTs only if grade ≥ 3

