9.2.2 Treatment emergent adverse events (TEAEs)

Treatment-emergent AEs (TEAEs) are defined as AEs with onset date/time at or after the start date/time of the first intake of pracinostat /placebo, or AEs with onset date/time prior to start date/time of the first intake of pracinostat/placebo that worsen in severity after the start date/time of the first intake of pracinostat /placebo, up to the end of the observation period. The observation period is defined as 30 days after the last dose of pracinostat/placebo or start of a new therapy for AML, whichever occurs first. TEAEs will be summarized by treatment group.

Where dates and/or times are missing or partially missing, AEs will be considered treatment emergent, unless there is clear evidence (through comparison of partial dates and/or times) to suggest that the AE started prior or after the study period.

The following tables will be produced:

- An overview summary of TEAEs by treatment group, including counts and percentages of patients as well as the number of events. The summary includes the following kinds of AEs:
 - any TEAE;
 - TEAEs by worst NCI CTCAE grade (only number of patients and %)
 - TEAEs by NCI CTCAE grade
 - TEAEs causally related to study drug / AZA / study drug or AZA (i.e either component of the study treatment);
 - TEAEs leading to permanent discontinuation of study treatment;
 - TEAEs leading to interruption of study treatment (separately for study drug and AZA)
 - TEAEs leading to dose reduction
 - SAEs;
 - SAEs causally related to study drug / AZA / study drug or AZA;
 - fatal SAEs;
 - fatal SAEs causally related to study drug / AZA / study drug or AZA
 - TEAEs of special interest
 - TEAEs of special interest related to study drug
- The number and percentage of patients reporting TEAEs will be provided by treatment group, System Organ Class (SOC), Preferred Term (PT), worst NCI CTCAE grade, and total. TEAEs will be sorted by SOC and PT in alphabetical order (SOC and PT within SOC).
- The number and percentage of patients reporting TEAEs together with the number of AEs, will be provided by treatment group, SOC, PT, and total. Similar table will be provided including only ≥ 3 worst NCI CTCAE grade. TEAEs will be sorted by frequency (based on column Total of all AEs) of a SOC and the PTs within a SOC.
- The number and percentage of patients reporting study drug (pracinostat / placebo) related (as classified by investigator) TEAEs will be provided as described for “all

-

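### The AE summary record has no first-dose cut-off, so an event that began before dosing and worsened on treatment can carry its pre-dose seriousness, and under one reading its pre-dose grade, into the TEAE tables

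*SAP*

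**What the plan says.** Protocol 8.2 requires the recording of "All adverse events occurring from the informed consent signature until 30 calendar days after last study drug (pracinostat/placebo) intake", with an earlier stop if new AML therapy starts. A later change of grade is entered as a follow-up of the initial event, not as a new event (Protocol 8.2 and 8.2.5.2).

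SAP 6.4 describes the resulting data structure: "recording one initial record and one record for each change in seriousness and/or severity within the same occurrence of the event". It then states: "A summary record will be derived aimed at being used for the production of the summary tables, while individual records will only be listed". On how that record is filled: "The summary record will pick-up among the collected records relevant to the same event" "the maximum seriousness and the maximum severity. Actions taken will be picked up from all the records". Different fields may come from different records. No date limit is given.

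Entry to the TEAE tables is decided separately. SAP 9.2.2 includes "AEs with onset date/time prior to start date/time of the first intake of pracinostat/placebo that worsen in severity after the start date/time" of first intake. SAP 9.2.1 treats an event that began before first dose and did not worsen as a pre-treatment AE, which is only listed. Protocol 8.1.1.5 says that "AEs with onset before the patient receives Dose 1 of study drug are considered as pre-treatment AEs", but the same paragraph counts a pre-existing event that worsens as a TEAE. Neither document names the grade against which worsening is judged.

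**The concern.** The entry rule asks whether something got worse after first dose. The summary rule then reports the worst thing that happened at any time in the occurrence. For an event that spans first dose the two can disagree: the row exists because of a modest on-treatment worsening, while the seriousness or grade shown in it arose before any study drug.

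The tables exposed are TEAEs by worst grade, the Grade 3 or higher tables, treatment-emergent SAEs, and the adverse events of special interest. SAP 6.4 makes membership of some special-interest categories (pneumonia, cytopenias, haemorrhage) conditional on Grade 3 or higher, so a carried-over grade could create a special-interest event as well as mis-grade one.

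The trial offers some opportunity for this. Uncontrolled infection is an exclusion (Protocol 3.4.2), so a screening infection has to come under control before entry and could later flare. One hypomethylating course within 30 days before Day 1 is permitted, and SAP 5.2 anticipates randomised patients who had such a cycle during screening.

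**Working it through.** The plan states no figure on this point, so there is none to reproduce. The check applies the SAP rules to every possible grade history of an event with onset before first dose.

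**Notation (Grades 1 to 4)**
- P = highest grade before first dose
- L = last grade before first dose, with L ≤ P
- T = highest grade on treatment

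There are 10 (P, L) pairs and 4 values of T, so 10 × 4 = 40 patterns. Grade 5 is left out: a fatal on-treatment event is its own maximum and cannot be mis-graded this way.

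**Rules applied**
- Tabulated grade under SAP 6.4 = max(P, T).
- On-treatment grade = T, so the table is wrong when P > T.
- TEAE status needs worsening after first dose. Two readings were run because the reference grade is not named.

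| | Worse than last pre-dose grade (T > L) | Worse than pre-dose peak (T > P) |
|---|---|---|
| Patterns that become TEAEs | 20 of 40 | 10 of 40 |
| Tabulated grade comes from a pre-dose record | 4 | 0 |
| Of these, false Grade ≥3 (P ≥ 3, T < 3) | 2 | 0 |

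The four patterns (P, L, T) are (3,1,2), (4,1,2), (4,1,3) and (4,2,3). The first two give a false Grade 3 or higher TEAE. The last two report Grade 4 when the on-treatment peak was Grade 3.

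**Patterns with a pre-dose peak of Grade 3 or 4, first reading.** There are 28. Of these, 16 never become TEAEs and are only listed. Of the 12 that do, 8 have T ≥ P and are graded correctly. The remaining 4 are those above.

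**Seriousness.** This does not depend on the reading of worsening. Take an event that is Grade 2 and serious before first dose, then Grade 3 and non-serious on treatment. It has worsened against both the last and the peak pre-dose grade, so it is a TEAE. The maximum grade, 3, is correct. The maximum seriousness is serious, so it is tabulated as a treatment-emergent SAE although it was never serious on treatment. The SAP foresees separate records for changes in seriousness, so this history can be represented in the data.

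**After the change.** If the maximum is taken only over records on or after first dose, the tabulated grade equals T in all 40 patterns, and pre-dose seriousness no longer enters.

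**The case against.** The strongest objection is that the SAP never says pre-dose records are included. The description in SAP 6.4 opens by speaking of how each TEAE is collected, which could mean on-treatment records only. That does not stand. The same section counts a worsening pre-existing event as a TEAE, and for such an event the initial record is necessarily pre-dose.

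Second, the severity error depends on the reference grade. That is correct: against the pre-dose peak it disappears. The last pre-dose grade is the more natural reading, because SAP 6.4 defines baseline as the most recent assessment before first dose, but the SAP does not apply that definition to AE grades. The seriousness error survives either reading.

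Third, the conditions are narrow. This stands. The records must belong to one unbroken occurrence; an episode that resolved and recurred is a different one. Clinically significant laboratory abnormalities at screening are not AEs (Protocol 6.2.4), and expected cytopenias are AEs only under listed conditions (Protocol 8.2.5.3), which shields much of the cytopenia category. Many patients would reach Grade 3 or higher anyway: Protocol 1.3 reports Grade 3 or higher thrombocytopenia in 46% and febrile neutropenia in 44% in Phase II. The row for any Grade 3 or higher event would therefore move less than individual preferred-term or SAE rows.

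Fourth, the individual records stay visible in Listing F9. This also stands: the error can be traced there, though not seen in the tables.

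**Conclusion.** Wrong as written, minor. Followed literally, SAP 6.4 tabulates pre-dose seriousness as a treatment-emergent SAE whenever the event worsens in grade on treatment without being serious there. It also tabulates a pre-dose grade in 4 of 20 TEAE patterns if worsening is judged against the last pre-dose grade, and in 0 of 10 if judged against the pre-dose peak. The pattern counts treat each history as one logical case and say nothing about how often it occurs. The documents give no count of AEs open at first dose, so no frequency can be computed.

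Three stronger readings are tempting and are not supported:

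- *That any Grade 3–4 or serious episode before treatment is reported as treatment-emergent.* SAP 9.2.1 only lists events that do not worsen.
- *That a rate of false Grade 3 or higher events can be put on this.* Every input would be invented.
- *That the rule dilutes the difference between arms.* It is the same in both arms. Equal false counts leave a risk difference unchanged and pull only a ratio towards 1. If one arm had more on-treatment worsening, it would also collect more false counts. The direction of any effect on the comparison is not determined, and the safety tables are descriptive, so no test is affected.

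**What to change.** In SAP 6.4, for events with onset before the first pracinostat/placebo dose, take maximum severity and maximum seriousness only over records dated on or after that dose and within the observation period defined in SAP 9.2.2. Leave the pre-dose records in Listing F9. In SAP 9.2.1 and 9.2.2, state that worsening means a grade higher than the last grade before first dose.

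The two changes belong together: naming the last pre-dose grade without the date condition would fix the reading under which the severity error occurs. The cost is one date condition in the derivation. The SAP already relies on the time order of the records when it takes the outcome from the last one, so no new data are needed, and the efficacy analyses are untouched.

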8.2.6 Adverse Events of Special Interest

Adverse events of Special Interest are defined as pre-specified AEs, serious and non-serious, under ongoing monitoring by the Sponsor.

No specific reporting timelines or other activities are required by the Investigator in addition to the normal AE reporting practices as described in the above sections for the followings AE of special interest:

- Supraventricular arrhythmias
- Sepsis, septic shock, grade ≥ 3 lung infection (pneumonia)
- Any infection leading to death
- Grade ≥ 3 anemia, neutropenia, febrile neutropenia and thrombocytopenia
- Grade ≥ 3 haemorrhage

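### The SAP's infection row for adverse events of special interest is labelled as including every fatal infection, but its retrieval rules pick up only those coded to certain terms

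*SAP*

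**What the plan says.** Protocol 8.2.6 lists "Any infection leading to death" as its own bullet, apart from the bullet for sepsis, septic shock and lung infection of Grade 3 or higher. SAP 6.4 commits itself to that list: "Adverse events of special interest (as described in the study protocol) will be retrieved according to the following rules". Its table merges the two infection bullets into one row, whose label ends "lung infection (pneumonia), any infection leading to death".

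The row retrieves events in three ways:

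- by standardised query: "Toxic-septic shock conditions (SMQ) - NARROW";
- by a word in the preferred term (PT): "Any PT that includes the word sepsis";
- by two named terms: "Exact match to the PT pneumonia or lung infection".

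The comment column adds one filter: "Pneumonia only if grade ≥ 3".

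**The concern.** The label promises a category defined by outcome, while the rules define it by term. A programmer who follows the rules will not retrieve a fatal infection coded to a term outside them, yet the output will carry a label saying that such events are included. SAP 9.2.2 presents AESIs by type and treatment group, so a reader comparing the arms would take the infection category as complete for fatal infections. Infection matters in this population: Protocol 4.2.2.1 reports febrile neutropenia (16%) and pneumonia (4%) among related serious events.

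**Working it through.** There is no planned figure to reproduce. The check sets the label against the rules and then follows an event through the outputs.

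**1. Label against rules (SAP 6.4, infection row).**

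| Part of the label | What puts it into effect |
|---|---|
| Sepsis | PT word rule |
| Septic shock | Narrow query |
| Lung infection (pneumonia), Grade 3 or higher | Exact-term rule plus the comment |
| Infection leading to death | Nothing keyed to death; covered only where one of the rules above happens to match the term |

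Three rules plus one comment make four criteria. Those that use fatal outcome, Grade 5 or the infections SOC: 0 of 4.

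**2. Can the label itself act as a rule?** The table's own practice is against it. Where a label carries a grade condition (infection, cytopenia and haemorrhage rows), the comment column restates it as a filter. Death is the only condition in a label that is not restated.

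**3. Is the rule elsewhere?** SAP 9.2, 9.2.2 and 9.2.7 list and tabulate AESIs without adding a retrieval rule. SAP 9.2.5 tabulates fatal serious events, but not as AESIs.

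**4. Could a term list be enough?** Protocol 8.2.1 has the site record, for a fatal case, the condition responsible for the death as the event term. The PT therefore depends on the infection, and a short fixed list cannot guarantee all of them. The pneumonia rule is also an exact match, so a longer pneumonia term would fail it.

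**5. What happens to a fatal infection outside the three rules?**

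- It is missing from the infection category in the SAP 9.2.2 tables by AESI type. There are at least five: two by worst grade (all, drug-related) and three by frequency (all, Grade 3 or higher, drug-related), 2 + 3 = 5. The two drug-related tables are affected only if the event is judged related or its relationship is missing.
- The by-cycle versions in SAP 9.2.7 are short in the same way.
- It is missing from the AESI overview rows (SAP 9.2.2) and Listing F13 (SAP 14) only if no other AESI row retrieves it. The cytopenia row, for instance, names *Neutropenic infection* at Grade 3 or higher.

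**6. The fatal cases described for the Phase II combination study.** Protocol 1.3 gives two related deaths among 50 patients, 2/50 = 4%: one neutropenic sepsis, one febrile neutropenia. Assume coding to those terms and a recorded grade of at least 3. Neutropenic sepsis then meets the sepsis word rule and is also named in the cytopenia row; febrile neutropenia meets the cytopenia row only. Retrieved as AESIs: 2 of 2. Retrieved by the infection row: 1 of 2. The Protocol describes only related deaths here, so this does not show how many fatal infections under other terms to expect.

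**The case against.** The strongest reply is that nothing goes unreported. SAP 9.2.5 tabulates treatment-emergent serious events resulting in death by arm, SOC and PT. The overview in SAP 9.2.2 counts fatal serious events, and Listings F11 and F14 show them and all deaths. Protocol 8.2.6 attaches no extra reporting duty to these AESIs. This stands, and it sets the size of the point. A reader might infer that fatal infections could disappear from the safety report; the documents do not support that.

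Two other strong readings also fail. One is that the fatal-infection AESI has no retrieval at all. In fact it is partly covered by term, and what is missing is a rule keyed to outcome. The other is that the AESI tables are incomplete. They would be incomplete only if a fatal infection is coded outside the rules, and the documents contain no such case.

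It is also fair to say that the contents of the named query are not given, so how much falls outside the rules is unknown. That limits any estimate of size but does not supply the missing outcome criterion.

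On the comment column, one can argue that label and Protocol treat lung infection and pneumonia as the same thing, so that the grade filter covers both. That is a reasonable reading, and the wording change below is therefore optional.

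**Conclusion.** The mismatch is real: the row's label includes all fatal infections, while its rules retrieve them only by certain terms. Severity is minor. The number of events affected cannot be computed from the documents and may be zero. The consequence, if such an event occurs, is an undercount in the infection category and possibly in the overall AESI outputs, all of them descriptive. No hypothesis test, significance level or power figure uses AESIs.

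The conclusion takes the named query to be a list of terms, as its name and its column in the table indicate. The Phase II check rests on the coding and grade assumed above.

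**What to change.** Add a fourth rule to the infection row: *any event in the infections SOC with fatal outcome or Grade 5*. Fatal outcome should be the main criterion, because the only description of Grade 5 printed in the Protocol (8.2.3, Table 3) is for events not listed in CTCAE. Optionally, extend the comment so that the Grade 3 limit names both pneumonia and lung infection, matching the label and Protocol 8.2.6.

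The cost is one table row and a re-run of the AESI flag. Outcome and maximum severity are already kept in the derived summary record (SAP 6.4), and SOC and grade are in the adverse event data (SAP 9.2). SAP 11 states that version 5 followed unblinding of the interim results, so the change should be declared there as made after the interim analysis.

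Two limits should be stated with it:

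- The rule sees only deaths recorded as an event outcome. Protocol 8.2 stops recording outcomes at the end of the reporting period and leaves unresolved events as ongoing, whereas 8.2.1 has serious events followed to resolution. The rule inherits that difference, so an infection fatal after the period may still be missed.
- Some events may count under two AESI types. Whether *Neutropenic infection* does depends on its MedDRA SOC, which the documents do not give. The SAP already allows such overlap, since *Neutropenic sepsis* meets the rules of two rows.

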3.3.3 Clinical Rationale

The combination of pracinostat plus AZA was evaluated in a Phase II open-label, single-arm, two-stage, multicenter study in patients aged ≥ 65 years with newly diagnosed AML (Study MEI-004). The favorable efficacy results of this study, with a CR rate of 42%, a composite complete remission (cCR) rate of 52%, and a median overall survival of 19.1 months, indicate that pracinostat plus AZA warrants further evaluation in a Phase III study in AML.

Data from the recent Phase III study of azacitidine versus conventional care regimens in 488 elderly patients with newly diagnosed AML revealed the following Grade 3 to Grade 4 treatment emergent AEs with azacitidine: febrile neutropenia (28%), neutropenia (26.3%), thrombocytopenia (23.7%), pneumonia (19.1%), anemia (15.7%) leukopenia (6.8%), and hypokalemia (5.1%) [Dombret, 2015]. Thus, when comparing safety data from studies of single-agent AZA, single-agent pracinostat, and pracinostat + AZA in combination, the safety profiles appear to be similar. Importantly, no new events of special interest were identified in the combination as compared to single-agent AZA or pracinostat studies, suggesting that the combination is not more toxic than single-agent therapies.

The observations of strong pre-clinical synergy between AZA and pracinostat, and the improved efficacy results from the Phase II study in AML compared to historical controls treated with AZA alone, suggest the combination may provide important clinical benefit in the defined patient population. The combination dose and schedule selected for Phase II development was pracinostat 60 mg orally, given 3 times a week, every other day for 3 consecutive weeks followed by 1 week of rest and repeated in 28-day cycles and azacitidine 75 mg/m² IV or subcutaneous (SC) for 7 days of each 28-day cycle. The same regimen will be evaluated in this Phase III study.

Collectively, these safety, tolerability, and clinical activity data support the testing of this combination dose and schedule in a pivotal, fully powered Phase III study in patients who are newly diagnosed with AML and who are not currently candidates for intensive induction chemotherapy.

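### The SAP retrieves the Grade ≥3 lung-infection AESI by exact match to only two preferred terms, which is narrower than the protocol's concept and out of line with the other AESI rules

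*SAP*

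**What the plan says.** Protocol section 8.2.6 lists the AESIs. The infection items are sepsis, septic shock, lung infection (pneumonia) of Grade 3 or higher and, as a separate item, any fatal infection.

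SAP section 6.4 makes its table the operative definition: "Adverse events of special interest (as described in the study protocol) will be retrieved according to the following rules reported in the table". One row carries all the infection items under the label "Sepsis, septic shock, grade ≥ 3 lung infection (pneumonia), any infection leading to death". That row gives three retrieval routes and one comment:

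- a standardised query, "Toxic-septic shock conditions (SMQ) - NARROW";
- a word search, "Any PT that includes the word sepsis";
- for the lung component, "Exact match to the PT pneumonia or lung infection";
- the comment "Pneumonia only if grade ≥ 3".

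SAP section 9.2.2 uses the resulting flag in the TEAE overview and in dedicated AESI tables by arm, type of AESI and PT.

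**The concern.** An AESI table should give the number of patients per arm who had the event the protocol defined. The protocol's lung-infection item is limited by grade but not by organism or type. The retrieval rule adds a limit of its own: the PT must be one of two exact strings. Protocol section 8.2.5.1 asks sites to record a diagnosis where one is known, which if anything favours specific terms over generic ones.

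Infection is a central risk of this regimen. Protocol section 3.3.3 cites 19.1% Grade 3-4 pneumonia with azacitidine in an earlier Phase III study. Protocol section 1.3 reports two deaths in the Phase II study considered related to both drugs, from neutropenic sepsis and febrile neutropenia. A grouped count that leaves out part of the severe pneumonias would describe this risk incompletely in the tables meant to summarise it.

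**Working it through.** No figure in the plan bears on this point, so the check sets the texts side by side and applies the rule as written.

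**Comparison of the rows in the SAP 6.4 table**

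| Component | How PTs are found | Grade comment |
|---|---|---|
| Sepsis | Word search, plus the narrow shock query | None |
| Lung infection / pneumonia | Exact match, two PTs | Names pneumonia only |
| Fatal infection | No rule given | None |
| Anaemia | Word search | Covers every listed PT |
| Neutropenia, febrile neutropenia, thrombocytopenia | Exact match to a list of 16 PTs (the list also holds a haemoglobin term) | Covers every listed PT |
| Haemorrhage | Word search on three words | Covers every listed PT |

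Exact matching is not unique to pneumonia. The cytopenia row also uses it, but with a long list that includes qualified terms such as neutropenic sepsis and neutropenic colitis. The lung component has neither a word search nor an extended list.

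**The rule applied to five cases**

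1. Grade 3, PT exactly pneumonia: retrieved.
2. Grade 3, PT consisting of pneumonia plus a qualifier, without the word sepsis: fails the exact match and fails the sepsis word search. Judged by its title, the shock query is not a pneumonia query; its contents are not in the documents. Not retrieved by any evident route.
3. The same event with a fatal outcome: inside the row label, because fatal infection is named there, but no query, PT or outcome rule acts on it. Not retrieved by any evident route.
4. Grade 1-2, PT pneumonia: excluded by the comment.
5. Grade 1-2, PT lung infection: included if the comment is programmed literally, excluded if the row label is followed. The text does not settle which.

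Cases 2 and 3 are the substance of the point. Case 5 is an ambiguity to be removed.

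**Where a missed event would still appear.** SAP section 9.2.2 tabulates all TEAEs by arm, SOC, PT and worst grade, with a further table for Grade 3 and above. Section 9.2.4 does the same for serious events, section 9.2.5 tabulates serious events resulting in death by SOC and PT, and section 9.2 lists all adverse events. The event is therefore reported, but under its own PT row. Such rows cannot be added up to patients, because one patient may contribute to several PTs, and a SOC total covers more than lung infection. No planned table then gives patients per arm with the protocol-defined event.

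**The case against.** Four objections deserve an answer.

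*The general tables already show everything.* Largely true, and it limits the point. A reader might infer that an excess confined to one organism would be lost to the safety analysis. The documents do not support that: such an excess would show by arm in the SOC/PT, Grade 3 and above, serious and fatal-event tables. What is lost is the grouped patient count.

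*The grade comment is adequate.* A reader might infer that Grade 1-2 lung infections are definitely counted. That goes too far. The row label and protocol section 8.2.6 treat lung infection and pneumonia as one concept limited to Grade 3 or higher. The comment also had to be worded more narrowly than in other rows, because extending it to every PT would wrongly restrict sepsis. The AESI tables show worst grade, and a version restricted to Grade 3 and above is planned, so a stray low-grade event would be visible. The wording is loose and needs tightening, no more.

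*The documents contain no pneumonia term list.* Correct. That MedDRA version 20.0 holds pneumonia PTs with other wording is an assumption, suggested by the qualified terms elsewhere in the table. The sponsor can confirm it in minutes.

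*AESI outputs are descriptive.* Also correct. Protocol section 8.2.6 attaches no special reporting duty to these events.

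What survives is the mismatch between the protocol's concept and the rule, and the inconsistency with the neighbouring rules.

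**Conclusion.** The point holds in a limited form. As written, the retrieval rule is narrower than the AESI it implements, and any Grade 3 or higher pneumonia under another PT would drop out of the grouped AESI tables. The grade comment is ambiguous for the PT lung infection, and the fatal-infection component has no rule at all.

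The size cannot be derived. A reader might multiply the 19.1% in protocol section 3.3.3 by 250 per arm (half of the planned maximum of 500), obtain 0.191 × 250 = 47.75, or about 48, and take some share of it as missed. The documents support none of these steps. The 19.1% comes from another study and is not said to be a single term or a group of terms; if it is a single term, differently worded pneumonias would come on top of it. The 250 is based on maximum enrolment, not on the Safety set. No document gives the share of severe pneumonias coded to other PTs.

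The conclusion rests on two assumptions: that such PTs exist in the dictionary version used, and that the shock query does not contain them. The effect is confined to descriptive safety outputs.

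**What to change.** Amend the infection row of the SAP 6.4 table:

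- replace the exact match with any PT containing the word pneumonia, plus a pre-agreed list of lung-infection PTs, and review the hits so that any non-infectious term is removed;
- state that the Grade 3 or higher limit applies to every lung-infection term and not to sepsis;
- add a rule for fatal infection based on the event's outcome.

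SAP section 11 says that version 5 followed unblinding of the interim results. The list should therefore be settled by staff without access to by-arm adverse event data, before the final AESI tables are run, and recorded as a change in that section.

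The cost is a small amount of term review and reprogramming of one flag. No new data are needed.
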